9.2. Variables

[figure not shown]
From the final sample, the following measures will be reported (Figure 2):

1. Patients with a claim for the respective treatment (apixaban for apixaban cohort or warfarin for warfarin cohort; using NDC from LRx) as their first post-discharge outpatient treatment (on or within 30 days following discharge i.e. discharge date or ≤ 30 days after discharge date) (n, %). These patients will comprise the analytic cohort for outcomes assessment.

- a. The date of the first post-discharge outpatient prescription claim in LRx (apixaban or warfarin) will be defined as the ‘treatment index date’ for patients in both cohorts respectively.
 - b. Patients will be required to have pharmacy stability during the 6-month period preceding the treatment index date, defined as consistent reporting of data in each month from the pharmacy associated with the treatment index date in LRx to ensure continuous visibility within LRx. The number of patients excluded due to lack of stability will be reported (n, %)
 - c. Patients with recurrent VTE, major bleeding, or CRNM bleeding between the discharge date and the treatment index date will be excluded. The number of patients excluded due to these reasons will be reported (n, %).
 - d. Patients will be followed from the treatment index date until the earliest of last prescription, last patient medical claim, end of pharmacy stability, or end of study period using the Dx/Rx databases.
2. Patients with OAC (warfarin, apixaban, rivaroxaban, dabigatran, or edoxaban) other than the respective inpatient treatment as their first outpatient prescription claim (on discharge date or within 30 days of discharge) (NDC codes from LRx; n, %). These patients will be captured as having switched from inpatient therapy and will not be further evaluated for outcomes.
 3. Patients with no post-discharge outpatient prescription claim for any OAC (on or within 30 days of discharge) (NDC from LRx; n, %)

All study outcomes will be evaluated for the apixaban and warfarin cohorts.

Figure 2. Study Flow

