2. Understand the post-discharge treatment patterns (including persistence, switch, and discontinuation) among patients who started on apixaban or warfarin in the hospital

The secondary objective is to:

3. Assess recurrent VTE, major bleeding, and clinically relevant non-major (CRNM) bleeding among patients who continue on apixaban or warfarin in the outpatient setting while persistent on index therapy

Study design

A retrospective database analysis will be conducted among patients hospitalized with a primary diagnosis of VTE. This study will utilize linked data from IQVIA's hospital charge master data (CDM), professional fee claims (Dx) and prescription claims (LRx) from 01 July 2017 through 31 December 2022 or the latest available data at the time of extraction (i.e., the *study period*), including 6-month pre-hospitalization period (starting the day before the admit date of hospitalization and a minimum 1-month post-hospitalization (starting a day after discharge date of hospitalization) period. The first apixaban or warfarin treatment during the index hospitalization will be flagged. Following discharge, patients who continue apixaban or warfarin, respectively, in the outpatient setting (with outpatient treatment claim occurring on or within 30-days following the discharge date) will be identified. The date of the first apixaban or warfarin claim will serve as the treatment index date. The baseline period will be 6 months prior to the treatment index.

Population

The study cohorts will be identified during the selection window from 01 January 2018 to 30 November 2022. Based on the treatment (apixaban or warfarin) received during the VTE hospitalization, patients will be classified into apixaban and warfarin cohorts. Patients will be required to have medical and pharmacy activity during the 6 month pre-hospitalization period and 1-month post-hospitalization period i.e. post-discharge. Following discharge, patients will be indexed to either apixaban or warfarin based on the first observed outpatient pharmacy claim for the respective therapy, and will have a 6-month baseline period prior to the treatment index date and a variable follow-up period after the treatment index date. Treatment patterns and clinical outcomes will be evaluated during the variable follow-up period.

Variables

Exposures and explanatory variables on the treatment index date and 6-months prior to the treatment index period (which includes the hospitalization)

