9.1. Study period and study design

The analysis will be conducted using data from 01 July 2017 through 31 December 2022 or the latest available data at the time of extraction (i.e., the *study period*). Figure 1 illustrates the study schematic for this project. The study cohorts will be identified during a selection window from 01 January 2018 to 30 November 2022. The date of the first treatment with apixaban or warfarin during the hospitalization will be flagged. Based on this treatment during the VTE hospitalization, patients will be classified into the apixaban and warfarin cohorts. Patients will be required to have medical and pharmacy activity during the 6 months prior to the admit date of the hospitalization (pre hospitalization period) and 1-month (minimum) from the discharge date of the hospitalization (post hospitalization period). The date of the first outpatient prescription for apixaban or warfarin on or within 30 days after discharge date from the hospitalization will be termed as ‘treatment index date’.

Figure 1. Study Period

*Latest available data at the time of extraction will be utilized for this study

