9.1.2. Exclusion criteria

Patients meeting any of the following criteria will be excluded from the study:

1. Patients with hospitalization with a primary diagnosis of VTE in the 6-month pre hospitalization period
2. Patients with any OAC administration other than apixaban for apixaban cohort (except warfarin use before apixaban) or warfarin for warfarin cohort during hospitalization

Note: Apixaban cohort patients will be allowed to have warfarin prior to apixaban administration. At this step, we will also report the number of patients that have both apixaban and warfarin use during the hospitalization.

3. Patients with unfractionated heparin or low molecular weight heparin (LMWH) administration after apixaban (for apixaban cohort) or warfarin (for warfarin cohort) administration during hospitalization.

Note: that unfractionated heparin or LMWH prior to apixaban or warfarin will be allowed.

4. With ≥ 1 claim/record with a diagnosis code for atrial fibrillation/flutter in Dx or CDM during the hospitalization and in the 6-month pre hospitalization period
5. With ≥ 1 claim with a procedure code for mechanical heart valve in Dx or CDM during the hospitalization and in the 6-month pre hospitalization period
6. With ≥ 1 claim with a procedure code for inferior vena cava filter in Dx or CDM during the study period
7. With ≥ 1 claim with a diagnosis code or procedure code of pregnancy in Dx or CDM during the study period
8. With use of OAC or PAC (in LRx or Dx) (unless prophylactic) during the 6-month pre-hospitalization period

Note: The OAC or PAC prescription claim will be considered prophylactic if duration of the prescription is ≤ 42 days AND the start date of OAC or PAC occurs within 2 days before or 7 days after knee/hip replacement surgery

OR

Start date of OAC or PAC occurred within 7 days after the admission of a hospitalization associated with 'medically ill' (primary discharge diagnosis; codes provided separately) AND with a ≥ 3 -day length of stay of the hospitalization.

9. With data quality issues (invalid/missing enrollment dates, gender and payer type)

A preliminary attrition table will be provided to the Alliance for review, at which time modifications to the inclusion and exclusion criteria may be considered.

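### Anticoagulant pharmacy claims dated during the index stay fall in neither claim window, so patients supplied before the discharge date are counted as having no claim, indexed late or dropped

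*Combined protocol and SAP*

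**What the plan says.** The plan reads outpatient anticoagulant claims in two windows.

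- **Before the stay.** Section 9.1.2, exclusion 8 removes patients "With use of OAC or PAC (in LRx or Dx) (unless prophylactic) during the 6-month pre-hospitalization period". The Abstract defines a "6-month pre-hospitalization period (starting the day before the admit date of hospitalization", counted backwards, so its last day is the day before admission.
- **After the stay.** Section 9.2, item 1 takes LRx claims dated "on or within 30 days following discharge i.e. discharge date or" up to 30 days after it. Section 9.1 uses the same window for the treatment index date: "The date of the first outpatient prescription for apixaban or warfarin on or within 30 days after discharge date from the hospitalization". Item 2 (switched) uses these dates too, and so does item 3: "Patients with no post-discharge outpatient prescription claim for any OAC (on or within 30 days of discharge").

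Two further rules depend on the second window. Under item 1a, "The date of the first post-discharge outpatient prescription claim in LRx (apixaban or warfarin) will be defined as the" treatment index date. Under item 1c, "Patients with recurrent VTE, major bleeding, or CRNM bleeding between the discharge date and the treatment index date will be excluded", with the number reported.

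The rules for the stay itself concern drug administered in hospital. Inclusion 2 flags the first administration, and exclusion 2 removes "Patients with any OAC administration other than apixaban for apixaban cohort" (prior warfarin being allowed), with a parallel rule for warfarin. Inclusion 6 separately requires at least one Dx claim and one LRx claim, for any drug, in the month after discharge.

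**The concern.** A discharge prescription can be dispensed before the patient leaves, for example by delivery to the ward or collection by a relative. If the LRx claim is dated before the discharge date, no rule picks it up. The patient holds the drug at discharge, but the plan first sees a refill, or sees nothing within 30 days.

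The split into continued, switched and no claim is the direct answer to objective 2. Section 7 motivates the study by evidence that many patients fill no anticoagulant prescription after discharge. A rule that counts supplied patients as having no claim pushes that proportion upward. For patients indexed at a refill, early on-treatment time is lost, and the interval in which an event excludes the patient under item 1c grows from zero to as much as 30 days. That carries into persistent days, the incidence rates and the Cox models.

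**Working it through.** The plan states no figure on this point, so there is none to reproduce. The check covers window coverage, the consequence for a single patient, and an illustration of size.

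**1. Coverage of claim dates**

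| Date of LRx anticoagulant claim | Rule that uses it |
|---|---|
| Within 6 months, up to the day before admission | Exclusion 8 |
| Admission to the day before discharge | None |
| Discharge date (day 0) to day 30 | Section 9.2, items 1-3 |

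The 6-month baseline before the treatment index date does span the stay, but the medications listed in section 9.2.1 include no anticoagulants. Inclusion 1 requires discharge after the admission date, so every patient has at least one uncovered day.

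**2. What happens to one patient**

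Let S be the days' supply, k the days before discharge on which it was dispensed, and L the refill delay in days (negative if early). The refill falls on day S - k + L. The values of S, k and L are assumed.

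| S | k | L | Refill day | Result as written |
|---|---|---|---|---|
| 30 | 1 | 0 | 29 | Indexed on day 29 |
| 30 | 1 | 2 | 31 | No claim (item 3) |
| 30 | 2 | 0 | 28 | Indexed on day 28 |
| 30 | 2 | 5 | 33 | No claim (item 3) |
| 14 | 1 to 3 | -3 to 5 | 8 to 18 | Indexed on days 8-18 |
| 90 | 1 to 3 | -3 to 5 | 84 to 94 | No claim (item 3) |

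With k = 0 the claim falls on the discharge date and the patient is indexed on day 0. Any patient in the table with no LRx claim of any kind in the month after discharge is removed by inclusion 6 and never reaches item 3.

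**3. Illustrative size**

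Assumptions, none taken from the documents: true continuation 70%; a share f of true continuers fill during the stay, with f from 1% to 10%; half of these refill after day 30.

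Share leaving the continued group = 0.70 × f × 0.5

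- f = 1%: 0.70 × 0.01 × 0.5 = 0.35 percentage points
- f = 3%: 0.70 × 0.03 × 0.5 = 1.05 percentage points
- f = 10%: 0.70 × 0.10 × 0.5 = 3.5 percentage points

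The other half, the same number, would be indexed late. These figures take everyone affected to land in item 3. At the other extreme, inclusion 6 removes them all and the denominator shrinks too:

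- f = 1%: (0.70 - 0.0035) / (1 - 0.0035) = 69.89%, a fall of 0.11 points
- f = 10%: (0.70 - 0.035) / (1 - 0.035) = 68.91%, a fall of 1.09 points

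The result is proportional to the assumed half. If nobody refilled by day 30, as with 90-day supplies, 0.35 and 3.5 would become 0.7 and 7.0.

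**The case against.** The strongest objection is that nothing in the documents shows this happens often. They do not mention fills dated before discharge from the index stay, and the window already includes the discharge date, so drug dispensed on the day the patient leaves is captured. Only fills dated at least a day earlier are affected. This stands as a limit on size. It does not close the gap. The prophylaxis note to exclusion 8 already allows for anticoagulant starts within 7 days after admission to an earlier hospitalization, so dates of this kind were foreseeable.

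Three stronger readings are tempting, and the documents do not support them.

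- *The no-claim proportion will be overstated by several points.* No frequency is given, and at 1% the formula yields 0.35 points. Inclusion 6 also takes some of these patients out of the sample altogether.
- *Every event in the first month is deleted.* Section 9.2.2 counts recurrent VTE only from 7 days after discharge, so a VTE readmission on days 1-6 does not meet the definition. Item 1c also requires the excluded number to be reported. And a delay of about a month applies only to 30-day supplies.
- *Item 3 labels these patients untreated.* Its wording is that they have no post-discharge claim, which is literally true. The error arises when that group is read as not having filled.

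A simple remedy also invites an objection that stands. Apixaban-cohort patients may have received warfarin first. If the window opened at the first administration of either drug, an abandoned in-stay warfarin claim could make such a patient a switcher.

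**Conclusion.** The gap is real and follows from the written definitions: an LRx anticoagulant claim dated from admission to the day before discharge is used nowhere. A patient supplied a day or more early is put in item 3, indexed at a refill, or dropped by inclusion 6. The direction for continuation is downward.

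The size is unknown. Under the stated assumptions it is at most about 0.35-3.5 percentage points, less the patients removed by inclusion 6. That range illustrates the mechanism and should not be quoted as an expected bias. Late indexing affects persistence, follow-up time and the item 1c exclusions as well, again to an unknown degree. Because the split is a main result and the claims can be counted in the data, a rule and a reported count are warranted before programming.

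**What to change.** In section 9.2, items 1-3, also accept LRx anticoagulant claims dated from the first inpatient administration of the cohort-defining drug (apixaban for the apixaban cohort, warfarin for the warfarin cohort) to the day before discharge. Add these rules:

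- If there are several in-stay claims, use the last one before discharge.
- If the earliest LRx anticoagulant fill from discharge to day 30 is for a different anticoagulant, that fill decides the classification.
- For patients who continue on the basis of an in-stay claim, set the treatment index date to the discharge date and run days' supply from there. Take pharmacy stability (item 1b) and prescriber specialty (section 9.2.1) from the in-stay claim.
- Let the in-stay claim count toward the LRx activity requirement in inclusion 6.
- Report how many patients are classified this way, and show the continued/switched/no-claim split under the window as now written as a sensitivity analysis.

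The cost is a few sentences in 9.2, one in inclusion 6, and slightly more programming, because the index date and the index claim must be held separately. A few in-stay claims may be for prescriptions changed before discharge. The second rule catches those followed by a claim for another anticoagulant within 30 days, and the sensitivity analysis shows how much the rest could matter.

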9.1.1. Inclusion criteria

Patients must meet all of the following inclusion criteria to be eligible for inclusion in the study:

1. Patients with an inpatient hospitalization with admit date and discharge date between 01 January 2018 and 30 November 2022 (selection window) in CDM with a primary diagnosis of VTE

Note: The admit date of the first hospitalization with primary diagnosis of VTE during the selection window will be flagged. Only patients with overnight stays with discharge date after the admit date (to confirm inpatient stay with overnight admission) will be included in the study.

Note: Number of patients who died during hospitalization (identified from discharge disposition measure) will be reported and these patients will be excluded from the study.

2. With evidence of receiving apixaban or warfarin during the hospitalization

Note: The date of the record with first apixaban or warfarin administration during the hospitalization will be flagged as the start of apixaban or warfarin treatment. Patients will be assigned to the apixaban or warfarin cohort based on this treatment received during hospitalization.

3. With linkage to LRx between 01 July 2017 and 31 December 2022 (i.e. study period)
4. With linkage to Dx during the study period
5. With activity in the 6 months prior to the admit date of hospitalization, defined as ≥ 1 claim in Dx and ≥ 1 prescription claim in LRx (pre hospitalization period)
6. With activity in the 1-month after the discharge date of hospitalization, defined as ≥ 1 claim in Dx and ≥ 1 prescription claim in LRx (variable post hospitalization period)
Note: Patients will have a minimum 1-month post discharge period (to capture outpatient treatment)
7. With age ≥ 18 years on apixaban or warfarin administration date during index hospitalization

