9.2.2. Outcome measures

The following outcome measures are assessed post-discharge, and will be measured during the variable post-index period starting on the treatment index date for the apixaban and warfarin cohorts.

Treatment patterns

- Persistent days (mean, SD, median, IQR, min, max) will be reported for patients until they discontinue, switch or end of follow-up based on definitions below
- Patients discontinuing outpatient treatment of apixaban or warfarin, respectively (NDC codes from LRx; n, %)

Note: Discontinuation will be defined as the occurrence of a ≥ 30 day gap from the run-out of days' supply of the treatment (post-discharge) index prescription (i.e. apixaban or warfarin) to the date of the next claim for the respective therapy or with no other claims for the respective therapy. The date of the discontinuation will be defined as the last day of the days' supply of the last filled prescription.

- Time (in days) from treatment index date to discontinuation date (mean, SD, median, IQR, min, max)

Note: Kaplan-Meier (KM) curves will be generated to measure median time (and 95 % CI) to discontinuation.

- Patients switching to an OAC other than apixaban or warfarin, respectively (switched) (NDC codes from LRx; n, %)

Note: Patients will be considered to have switched if they filled a prescription for OAC other than apixaban or warfarin, respectively (identified through NDC codes in LRx) or for PAC within 30 days before or after the run out date of index treatment. The date of the switch will be defined as date of the prescription of such a therapy (OAC or PAC).

- Time (in days) from treatment index date to switch date, defined as the date of the first claim for the new OAC or PAC (mean, SD, median, IQR, min, max)

Note: KM curves will be generated to measure median time (and 95 % CI) to switching

Clinical Outcomes

The following clinical outcomes will be assessed during the time patients are persistent with their respective index apixaban or warfarin treatment (treatment index):

- Patients with ≥ 1 hospitalization for recurrent VTE (ICD-10 codes in CDM; n, %)
- Incidence rate (IR) of recurrent VTE (per 100 patient years)
 - The date of the first observed event will be flagged. The numerator for IR will be the number of patients with the event of interest and denominator will be the ‘at risk’ period i.e. the time to first event. The 95% confidence intervals (CI) will also be reported.

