9.6. Data analysis

Descriptive statistics will be produced for all relevant study measures previously described, for the overall cohort and for each treatment (apixaban and warfarin). Categorical measures will be presented using frequency (number of patients [n]) and percentage (%) of total study patients observed in each category. Continuous and count variables will be presented as the mean, SD, median, minimum, maximum and IQR. As relevant, continuous variables will also be categorized into intervals. Univariate statistics will be calculated for each measure of interest. No comparisons will be made between the two cohorts..

Four multivariable regression models will be developed for this study. Cox proportional hazards models will be conducted to evaluate both the risk (expressed as hazard ratios with corresponding 95% confidence intervals) of discontinuing or switching from the index treatment as well as the risk of experiencing a clinical event (i.e., recurrent VTE, major bleeding, or CRNM bleeding).. The main effect variable will be the treatment cohort (apixaban vs. warfarin, with warfarin as the reference group). Covariates to be considered for inclusion into the models will include demographic and clinical characteristics of interest. A backward elimination of independent variables least associated with the dependent variable may be used. Clinically relevant covariates that are not retained during backward elimination may also be forced into the model. Collinearity among the variables of interest will be evaluated during model development.

Kaplan-Meier analyses will also be utilized to report the time to an event of interest (e.g., switch, discontinuation). Kaplan-Meier is a method for estimating the probability of the proportion of individuals remaining in the sample at a particular time from an initiation point. It takes into account patients lost or censored before the study endpoint. All analyses will be based on observed, not projected, data. Analyses will be conducted using SAS[®] Release 9.4 (SAS Institute Inc., Cary, NC), and the results will be reported in Excel tables.

Any major modifications of primary endpoint definitions (treatment patterns) or their analyses would be reflected in a protocol amendment.

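### The end-of-follow-up rule in section 9.2 item 1d is not reconciled with the run-out-dated discontinuation in section 9.2.2, so some final-fill stops drop out of the primary endpoint and others may count without an observed 30-day gap

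*Combined protocol and SAP*

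**What the plan says.** - **End of follow-up (section 9.2, item 1d).** Observation starts at the first outpatient index fill and runs "until the earliest of last prescription, last patient medical claim, end of pharmacy stability, or end of study period using the Dx/Rx databases". Neither the drug nor the date type (fill or run-out) of the last prescription is given.
- **Discontinuation (section 9.2.2).** The event is a gap of at least 30 days from run-out to the next index-drug claim, "or with no other claims for the respective therapy. The date of the discontinuation will be defined as the last day of the" supply of the last fill.
- **Persistent days (section 9.2.2).** These "will be reported for patients until they discontinue, switch or end of follow-up based on definitions below". End of follow-up is in fact defined only in item 1d.
- **Time to discontinuation (section 9.2.2).** Kaplan-Meier "curves will be generated to measure median time (and 95 % CI) to discontinuation".
- **Switching (section 9.2.2).** Another OAC or a PAC filled "within 30 days before or after the run out date of index treatment" counts as a switch.
- **Activity (section 9.1.1, criterion 6).** "With activity in the 1-month after the discharge date of hospitalization, defined as ≥ 1 claim in Dx" and at least one in LRx. The month runs from discharge, not from the index date.
- **Pharmacy stability (section 9.2, item 1b).** Patients are "required to have pharmacy stability during the 6-month period preceding the treatment index date", meaning monthly reporting by the index pharmacy.
- **Status of the endpoint (section 9.6).** "Any major modifications of primary endpoint definitions (treatment patterns) or their analyses would be reflected in a protocol amendment".

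**The concern.** Item 1d ends observation on the date of some claim. Section 9.2.2 places the event at the end of a supply period, which usually falls after the claim that started it, and needs a further 30 days to confirm it. Nothing says what happens when run-out falls after the item 1d date, or when fewer than 30 days are observed after run-out.

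The two rules agree for a patient with LRx and Dx claims well beyond run-out. They disagree for patients whose claims stop early, and those patients include many who have just stopped treatment. Follow-up duration, persistent days, the percentages discontinuing and switching, and the Kaplan-Meier medians all depend on this date. Two programmers could follow the text and get different primary results from identical data.

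**Working it through.** The plan gives no figure on this point to reproduce. The check is date arithmetic, followed by an illustrative simulation.

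**1. Convention.** Day 0 is the treatment index date. Last covered day = fill day + days' supply − 1, following section 9.2.2.

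**2. Two readings of the last prescription.** Take 30-day index fills on days 0, 30 and 60. The last covered day is 60 + 30 − 1 = 89.

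| Reading (fill date) | Follow-up ends | Stop dated day 89 |
|---|---|---|
| Index drug | day 60 | outside follow-up by 29 days; true of every final 30-day fill |
| Any LRx claim, last other fill on day 75 | day 75 | outside follow-up by 14 days |
| Any LRx claim, other fills well after day 89 (and Dx claims too) | after day 89 | inside follow-up |

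Under the any-LRx reading, one index fill with no later LRx claim gives 0 days of follow-up.

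**3. The Dx limb.** Because the earliest date governs, a last Dx claim on day 40 ends follow-up on day 40 even if index refills continue. If the only Dx claim is 5 days after discharge and the first outpatient fill is 20 days after discharge, criterion 6 is met, yet follow-up ends 20 − 5 = 15 days before it starts.

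**4. Switching.** Under the any-LRx reading a switch fill is itself an LRx claim, so only the Dx limb can hide it. Under the index-drug reading, a switch after run-out is always outside follow-up.

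**5. Data end at 31 December 2022.**
- A 30-day fill on 2 November is covered to 1 December, and 30 more days reach 31 December. The gap can just be observed.
- A fill on 3 November is covered to 2 December, and 30 more days reach 1 January 2023. The gap cannot be observed.
- A fill on 2 December is covered to 31 December. Later fills run out after data end.
- The affected fills are therefore 3 November to 2 December, which is 28 + 2 = 30 dates. Possible index dates run from 2 January 2018 to 30 December 2022 (30 November + 30 days), which is 1,824 dates. 30 / 1,824 = 1.6%.

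**6. Direction.** A patient who fills nothing else and stops is censored at the final fill, just before the event. A patient who keeps refilling is not. This censoring is informative: it lowers the percentage discontinuing and raises the Kaplan-Meier curve. Persistent days move the other way, because an earlier end date can only shorten the count or leave it unchanged (75 instead of 89 in step 2).

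**7. Illustrative size.** None of these inputs is in the documents. Assumed: 30-day fills; stopping probability q = 0.15 per fill; 20% refill 60 days after run-out; 10% fill no other drug and the rest fill one every 30 days; Dx claims at random with mean gap 30 days, plus one within 30 days of discharge; half fill on the discharge day and the rest 0 to 30 days later; window uniform over 31 to 1,826 days; 400,000 patients per scenario. True persistence beyond day 180 is 0.85^6 = 0.377. The true median is 150 days (0.85^4 = 0.522, 0.85^5 = 0.444).

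Each cell gives % discontinuing / proportion beyond day 180 / median days.

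| Scenario | Truth beyond day 180 | Item 1d, any LRx | Fixed window, observed gap |
|---|---|---|---|
| Base | 0.377 | 81.6 / 0.406 / 150 | 88.9 / 0.384 / 150 |
| 5% fill no other drug | 0.377 | 85.2 / 0.392 / 150 | as base |
| 30% fill no other drug | 0.377 | 67.3 / 0.471 / 180 | as base |
| q = 0.10 | 0.531 | 76.5 / 0.558 / 240 | 83.4 / 0.537 / 210 |
| q = 0.20 | 0.262 | 84.1 / 0.289 / 120 | 91.7 / 0.269 / 120 |

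- Of confirmed discontinuations, item 1d loses 8.7% (4.7% and 24.7% when 5% and 30% fill no other drug). This mostly restates that assumed share.
- Zero-day follow-up is 1.2% in the base case.
- Among counted discontinuations, 1.8% have no observed gap inside follow-up.
- In a run with similar inputs, mean persistent days were about 178 under item 1d against 184.
- A different assumed model takes only true final-fill stoppers, with the last LRx and last Dx claims each exponential with mean 90 to 365 days after the final fill, and supplies of 14 to 90 days. It puts run-out after the end of follow-up in 8% to 87% of them.

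**8. Unobserved exit.** Section 9.8 says mortality is not captured. Proportion beyond day 180, truth 0.377:

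| Exit per year | Item 1d | Fixed window | Later of last LRx and last Dx claim |
|---|---|---|---|
| 15% | 0.407 | 0.358 | 0.399 |
| 30% | 0.408 | 0.333 | 0.411 |

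**The case against.** The strongest defence is that ending follow-up at last activity is a recognisable response to open claims data without enrolment or mortality. Section 9.8 discloses both limits. At 30% unobserved exit a year, item 1d is off by 0.408 − 0.377 = +0.031, against −0.044 for the fixed window and +0.034 for the later-of window, so both alternatives do slightly worse. This stands: the choice of window is a judgement. It does not excuse an undefined term, follow-up that can end before it begins, or the lack of a stated gap rule.

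Four further objections stand in part.
- The 30-day gap may be meant to govern the no-further-claims branch as well. If so, and if the gap must be observed, the data-end case disappears. The text permits that reading but does not state it.
- The end of pharmacy stability can be inferred from item 1b as the month in which the index pharmacy stops reporting. It would help to say so, but it is not a gap of the same kind.
- The base-case median does not move, day 180 is not a time point in the plan, and the one-step median shifts reflect the assumed 30-day grid.
- Section 9.1 allows later data than 31 December 2022, which would move the data-end dates.

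A reader might infer more than the documents support.
- *Every final-fill discontinuation is lost.* This needs the index-drug reading. Item 1d sets the term beside the last medical claim and the Dx/Rx databases, which points to any LRx claim.
- *Persistence is overstated throughout.* Mean persistent days fall.
- *All late index dates are miscounted.* Fills after 2 December 2022 run out after data end and are not counted.
- *The apixaban-warfarin hazard ratios or the incidence rates are biased.* Nothing in the documents shows that the problem differs by cohort, and no change in incidence rates was computed.

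**Conclusion.** The point holds and should be fixed. Confidence is high that items in sections 9.2 and 9.2.2 are not reconciled; this can be seen from the text alone. Followed literally, the rule loses final-fill discontinuations whose last LRx or Dx claim precedes run-out, and it can give zero or negative follow-up. Whether it also counts stops without an observed gap depends on how the no-further-claims branch is read. At data end, that exposure is about 1.6% of possible index dates for 30-day fills.

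The percentage discontinuing is understated, Kaplan-Meier persistence is overstated, and mean persistent days are shortened. The true size is unknown. Under the main assumed inputs, where most patients keep filling other drugs monthly, it is about 7 percentage points on discontinuation (88.9 − 81.6 = 7.3) and 2 points on persistence beyond day 180 (0.406 − 0.384 = 0.022). It would be larger if claims after the final fill are sparse.

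**What to change.** 1. In item 1d, state that the last prescription means any LRx claim. Do not let a last LRx fill or last Dx claim end follow-up before run-out of index-drug supply already dispensed, or before the index date.
2. In the discontinuation note, count the event only if run-out plus 30 days falls inside the observation window. Otherwise censor at run-out or window end, whichever is first. Apply the same window to the 30 days after run-out in the switch definition.
3. Name the primary end-of-observation rule in advance. A fixed window counts unobserved deaths and exits as discontinuations; an activity-based window censors informatively. A sensitivity table under the other window is optional.

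Step 2 should not be adopted alone. With the earliest-of end date kept, requiring an observed gap gives 80.0% discontinuing and 0.425 beyond day 180 in the base case, further from the truth than item 1d as written. With the later of the last LRx and Dx claims it gives 88.2% and 0.387.

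The cost is rewording, a little reprogramming and, because these are primary endpoint definitions, an amendment of the kind section 9.6 foresees. No new data are needed. Fills near data end will be censored instead of counted, and no choice of window removes the bias from unobserved exits.
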